While we have described a 50% decrease in maturation failure as reasonable, at least one study of early postoperative ultrasound for maturation monitoring has shown results surpassing this figure. Muray Cases et al. used early ultrasonography to achieve a 78% maturation success rate. In almost all cases of incipient maturation failure, a single, correctible lesion was identified.(9) Remarkably, because of this early detection not a single patient initiated dialysis with a central venous catheter.(9)

Despite the obvious benefit of ultrasonography to reduce maturation failure, regular surveillance imaging of dialysis access is not routinely performed in the United States. Because of the onerous requirements for high trained technical staff, an interpreting physician, a fully equipped and certified vascular laboratory and the time and effort required to undergo formal ultrasound examination, responsible resource utilization precludes frequent formal scanning. In fact, meeting Medicare criteria for medical necessity for such imaging after the maturation study at six weeks requires documentation of quantifiable access malfunction occurring during dialysis or major clinical findings such as massive upper extremity swelling. This limitation is understandable in light of the economic burden associated with a lengthy Duplex examination of hemodialysis access. Ultrasound assessment of dialysis access entails the cost of a dedicated vascular laboratory, an ultrasound apparatus and a qualified ultrasound technologist. A full examination uses color Doppler imaging, pulsed-wave spectral Doppler imaging, and B-mode ultrasound. The patient burden is equally involved, requiring a separate appointment on an additional delay at a vascular laboratory that may be distant from the patient's dialysis center. The study yields a comprehensive assessment of the fistula and the potential to diagnose conditions ranging from aneurysmal degeneration to medial calcinosis and peripheral ischemia.

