Patients are free to withdraw consent at any time. Patients who wish to terminate their participation in the research will no longer receive EchoSure ultrasound examinations of their fistula and their data will be removed from the study.

8: STATISTICAL ANALYSIS

Stage 1:

We will recruit 60 patients for participation in this study who are planning to undergo elective construction of upper extremity autogenous hemodialysis access. The minimum sample size of 45 was determined assuming a 50% successful fistula maturation rate (based on past studies) to yield sufficient power to detect a difference in maturation between this cohort and the intervention cohort in the next aim. It also accounts for the quantity of patient volumes needed to develop a [REDACTED] based on our experience with EchoSure. Lastly, this provides sufficient power to detect a difference in fistula maturation success based on the flow rate (logistic regression power estimation; $\alpha = 0.05$, $\beta = 0.8$, OR 2.5 [from $\text{Pr}(H_0) 0.45$ and $\text{Pr}(H_1) = 0.65$]. As a buffer, based on institutional experience with clinical research and subject attrition a drop-out rate of 25% has been added to yield a total of 60 patients.

Using the EchoSure-derived conduit diameter and volumetric flow as observed values and Duplex-derived conduit diameter and volumetric flow as accepted values, the accuracy of EchoSure will be calculated. Logistic regression will be used to assess the correlation between successful maturation and EchoSure-derived values for flow and conduit diameter at two weeks. Cut points will be evaluated to establish EchoSure criteria for [REDACTED] [REDACTED]. Pearson's correlation will be performed on both EchoSure-derived and Duplex-derived values of volumetric flow and conduit diameter to determine correlation between EchoSure findings at two weeks and both EchoSure and Duplex findings at six weeks.

Stage 2:

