For this portion of the study, we will recruit an additional 60 patients planning to undergo elective construction of upper extremity autogenous hemodialysis access. Again, the EchoMark fiducial marker will be inset at the time of fistula creation. The minimum sample size of 45 (60 prior to 25% dropout factor) is powered to detect an approximate 25% reduction in all-cause fistula failure in the early postoperative period. A χ^2 power analysis was performed with $\alpha = 0.05$, $\beta = 0.8$ and standard-of-care fistula maturation success at 50% based on institutional experience and prior literature which ranges from 30-70% and EchoSure early intervention success based on the Muray-Cases results which showed a 78% success rate achieved by a novel program of pre-maturation ultrasonography and early intervention.

The nominal-by-interval association coefficient, Eta, will be calculated to determine the correlation between successful, unassisted maturation and EchoSure-derived values for flow and conduit diameter at two weeks. This will be compared to the similar findings of stage 1 using Student's t-testing and will validate the early maturation criteria derived from there. The association coefficient will be calculated to determine the correlation between successful, assisted maturation and EchoSure-derived values for flow and conduit diameter immediately following intervention. Pearson's correlation will be performed on both EchoSure-derived and Duplex-derived values of volumetric flow and conduit diameter to determine correlation between findings immediately following intervention and those at six weeks. [REDACTED]

Using χ^2 testing between the stage 1 and 2 cohorts, the benefit to maturation success of intervention based on early postoperative EchoSure examination will be determined.

9: PATIENT ENROLLMENT AND CONSENT

Method of Subject Identification and Recruitment

Patients will be identified and recruited by the surgeons participating in the study. Patients who have been scheduled for a fistula creation surgery will be identified as appropriate for study recruitment. The study details will be explained to identified patients and the consent process will begin for willing patients.

Informed Consent

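### Stage 2's 45 evaluable patients per stage detect a 28-point fall in failure, not the stated 25%; the Stage 1 odds ratio of 2.5 does not follow from its probabilities

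*Combined protocol and SAP*

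**What the plan says.** The plan makes three power statements in Section 8.

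- **Stage 2, effect.** The minimum of 45 "is powered to detect an approximate 25% reduction in all-cause fistula failure in the early postoperative period". The plan does not say whether the 25% is absolute or relative.
- **Stage 2, inputs.** The next sentence sets α = 0.05, β = 0.8 and standard-of-care success of 50%. It bases success under EchoSure-guided intervention on a cited study "which showed a 78% success rate achieved by a novel program of pre-maturation ultrasonography and early intervention". The number is given as "The minimum sample size of 45 (60 prior to 25% dropout factor)". The analysis it supports is χ² "testing between the stage 1 and 2 cohorts, the benefit to maturation success of intervention". Neither sidedness nor continuity correction is stated.
- **Stage 1.** The same minimum of 45 is meant "to yield sufficient power to detect a difference in maturation between this cohort and the intervention cohort in the next aim". It is also said to suffice for detecting a "difference in fistula maturation success based on the flow rate (logistic regression power estimation"), with α = 0.05, β = 0.8 and an odds ratio of 2.5 derived from probabilities of 0.45 and 0.65.

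Section 4 gives another effect size for the same outcome: "While we have described a 50% decrease in maturation failure as reasonable".

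**The concern.** Two adjacent sentences describe one Stage 2 calculation but give different effects. A rise in success from 50% to 78% is not a 25% reduction in failure on either the absolute or the relative scale. The odds ratio in Stage 1 is likewise not the one its own probabilities produce.

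Failed maturation is the Stage 2 primary performance endpoint (Section 5), and the stage 1 versus stage 2 χ² test is how the plan will judge benefit. The stated detectable effect is what a reader uses to interpret a non-significant result. If the study has 80% power only for 28 points but claims it for 25%, a null result would look like stronger evidence against a 25% reduction than it is. The Stage 1 power statement cannot be checked until its odds ratio and probabilities agree.

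**Working it through.** **Inputs (Section 8).** Control success p₁ = 0.50; intervention success p₂ = 0.78; α = 0.05; power 0.80 (written as β); 45 evaluable per stage; dropout 25%. Assumed because not stated: two-sided test, no continuity correction.

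**Step 1. Reproduce the plan's 45 and 60.** With p̄ = (p₁ + p₂)/2,

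n = [z_α √(2p̄(1 − p̄)) + z_power √(p₁(1 − p₁) + p₂(1 − p₂))]² / (p₂ − p₁)²

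Here p̄ = 0.64, so n = [1.960 × 0.6788 + 0.8416 × 0.6493]² / 0.28² = (1.3305 + 0.5465)² / 0.0784 = 44.93, which rounds up to 45. Then 45 / (1 − 0.25) = 60. Both figures reproduce. Exact binomial power of the uncorrected χ² test at 45 per stage is 80.9%.

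**Step 2. The effect behind 45.** Failure falls from 1 − 0.50 = 50% to 1 − 0.78 = 22%. That is 28 points, or 28/50 = 56% relative. Solving for the smallest p₂ detectable with 80% power at 45 per stage also gives 0.780.

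**Step 3. Power for the stated 25%.** Power = Φ{[(p₂ − p₁)√n − z_α √(2p̄(1 − p̄))] / √(p₁(1 − p₁) + p₂(1 − p₂))}.

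- 25 points (p₂ = 0.75): Φ{[1.6771 − 1.3419] / 0.6614} = Φ(0.507) = 69.4% (exact 70.1%).
- 25% relative (failure 37.5%, p₂ = 0.625): Φ{[0.8385 − 1.3750] / 0.6960} = Φ(−0.771) = 22.0% (exact 21.2%).

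| Success vs 50% | Fall in failure | Two-sided, 45 | Two-sided, 60 | One-sided, 45 |
|---|---|---|---|---|
| 78% | 28 points (56% relative) | 80.1% | 90.2% | 88.0% |
| 75% | 25 points (50% relative) | 69.4% | 81.6% | 79.8% |
| 62.5% | 12.5 points (25% relative) | 22.0% | 27.9% | 32.5% |

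For 80% two-sided power at 25 points, n = 57.67, so 58 evaluable; 58/0.75 = 77.3, so 78 enrolled per stage.

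**Step 4. Does sidedness reconcile the figures?** With one-sided 5%, 75% success needs 45.31 per stage, close to 45. But 78% success then needs only 35.28, so 36. Neither choice lets 45, 78% and exactly 25 points hold together.

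**Step 5. Stage 1 odds ratio.** (0.65/0.35) / (0.45/0.55) = 1.857 / 0.818 = 2.27. Rounding to two decimals does not explain 2.5: the most extreme values, 0.445 and 0.655, give 2.37. An odds ratio of 2.5 would need 0.672 (from 0.45) or 0.426 (to 0.65).

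For scale only, under a formula the plan does not state (continuous flow, odds ratio per standard deviation, event rate 0.45, two-sided), power at 45 is Φ(√(45 × 0.45 × 0.55) × ln OR − 1.96): 78% at 2.27 and 86% at 2.5.

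**Step 6. β.** Taken literally, β = 0.8 means 20% power, for which 50% versus 78% would need only 8 per stage. Power of 0.8 is plainly meant.

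**The case against.** The strongest defence is that the sample size is correct, its inputs follow in the next sentence, and the 25% is hedged as approximate. Read as loose wording for 28 points, the gap is only 3 points. That is a fair reading, and it confines the problem to the text. It does not remove it: those 3 points cost about 11 points of power (80.1% to 69.4%).

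The relative reading, with 22% power, can be said to be ruled out by the stated 78%. That is true for a reader who works it through. But Section 4 describes the same outcome with a relative figure, and the Stage 2 sentence does not say which scale it uses.

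It can also be said that 60 per stage are to be enrolled, and with all 60 evaluable the power for 25 points is 82%. That stands, but the plan ties its claim to 45 and expects to lose a quarter of patients.

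The plan does not state a two-sided, uncorrected test. The match at 45 supports that choice strongly, but the sponsor should confirm it.

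On Stage 1, the logistic statement is only one of the reasons given for 45, and the effect of the mismatch appears modest. If 0.45 and 0.65 had themselves been rounded to the nearest 0.05, the odds ratio could lie between 1.84 and 2.81, a range that includes 2.5. That is an assumption, and the plan presents 2.5 as following from the two printed figures. The β notation alone is clerical.

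**Conclusion.** The concern holds, and the text should be corrected. The 45 evaluable and 60 enrolled per stage are right for 50% versus 78% success. The effect they detect with 80% power is a 28-point (56% relative) fall in failure. At 45 per stage, a true 25-point benefit would be missed about 31% of the time (100% − 69.4%) rather than 20%.

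These figures assume a two-sided 5% χ² test without continuity correction, 50% failure in Stage 1, and evaluable numbers at the plan's minimum. The Stage 1 odds ratio is 2.27 from the printed probabilities, not 2.5, and the documents do not show which figure is the slip. The β notation is wrong in both stages but does not affect the sample size.

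**What to change.** Replace the Stage 2 power sentence, once the sponsor confirms the test used, with:

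> Forty-five evaluable patients per stage give 80% power (χ² test without continuity correction, two-sided α = 0.05) to detect maturation success of 78% versus 50%, i.e. failure of 22% versus 50% (28 percentage points, 56% relative). Power for a 25-point reduction (75% success) is about 69% with 45 per stage and 82% if all 60 are evaluable.

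For Stage 1, reconcile the odds ratio with 0.45 and 0.65. Then restate the power with the formula, the scale on which flow enters the model and the event rate assumed. In both stages, write power = 0.8 in place of β = 0.8.

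This is a text correction, and the sample size, test and endpoint stay as they are. The cost is that the stated detectable effect becomes less favourable. Numbers would change only if the sponsor wants 80% two-sided power for 25 points: 58 evaluable, or 78 enrolled, per stage.

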3. STUDY SUMMARY

Title:	Automated Ultrasound Flow Monitoring for Maturation of Peripheral Arteriovenous Fistulae
Protocol Number:	2019-1
Design:	
This is a prospective, single arm, non-randomized, multi-center observational study to demonstrate the performance of the EchoMark and EchoSure devices in patients undergoing peripheral arteriovenous fistula creation for hemodialysis access.
 
Stage 1: EchoMark implantation at the time of fistula creation with scheduled follow up for EchoSure imaging of the fistula maturation process. This stage will produce EchoSure criteria for early prediction of maturation failure.
 
Stage 2: EchoMark implantation and imaging with EchoSure to prove the robustness of the fistula maturation failure criteria established in stage 1 and measure the effect on ultimate fistula maturation rates.

Study Duration:	
Projected enrollment of first patient: May 2020
 
Projected exit of final patient: December 2021

Primary Objective:	
Stage 1: The primary objective of the study is to collect data to verify the technology's performance in monitoring fistula maturation and understand the natural history of AV fistula flow physiology.
 
Stage 2: The primary objective of the study is to assess the ability of the EchoMark and EchoSure system to reduce the rate of failed fistula maturation.

Patient Population:	Patients undergoing upper extremity autologous arteriovenous fistula creation.
Sample Size:	
Stage 1: Up to sixty (60) patients will be enrolled.
 
Stage 2: Up to sixty (60) patients will be enrolled.

Number of Sites:	To be determined
Treatments:	
Stage 1: EchoMark soft tissue marking devices will be placed and monitored using the EchoSure system for 24 weeks or confirmed fistula maturation/failure has been declared by the attending vascular surgeon, whichever comes first.
 
Stage 1: EchoMark soft tissue marking devices will be placed and monitored using the EchoSure system for up to 52 weeks. Upon the decision by the attending surgeon that the fistula failure is confirmed or that monitoring is no longer clinically necessary patients will exit the study

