Research has established that volumetric flow at six weeks after fistula creation correlates with flow at two weeks after creation.(11) This two-week marker has additional and substantial importance; two weeks postoperatively is accepted as the time at which fistula revision can be performed. Most revision surgeries and procedures do not disturb the primary fistula conduit. Taken together, these represent an opportunity to detect and treat maturation failure as early as two weeks postoperatively and enable a fistula to reach maturation by the expected date. Compared to the abovementioned 30-70% failure rate, regular early ultrasound surveillance has resulted in a success rate of 78%. In 2014 alone, such an improvement would result in the salvage of 25,000 – 70,000 fistulas.(12)

A single imaging modality, ultrasonography, is able to assess volumetric flow within a fistula and determine anatomic factors predisposing it to maturation failure or impending late failure. Duplex ultrasound, however, is a resource-intensive practice that requires the dialysis patient to make an additional visit to an outpatient imaging laboratory and requires a trained, formally certified professional ultrasonographer. The examination itself requires 45 minutes to an hour. It

is only complete after image interpretation by a physician which can take an additional 24-48 hours. The substantial commitment of material resources, time, and personnel make formal Duplex ultrasonography too costly for performance of frequent examination, despite the potential for economic and proven clinical and quality improvement that regular scanning holds.(9)

This potential is not theoretical. Doppler ultrasound imaging has demonstrated utility in predicting both fistula maturity and in detecting impending fistula thrombosis.(1, 9, 11, 13-19) Ultrasound criteria for the prediction of maturation failure have been established, and ultrasound can determine the cause of non-maturation and allow planning for surgical intervention.(1) Studies indicate that routine surveillance of fistulae can predict maturation and that a program of routine ultrasound surveillance decreases the rate of maturation failure significantly.(1, 9, 11, 16) A multicenter study of more than 500 upper extremity fistula creations determined that both fistula diameter and volumetric flow at two weeks postoperatively were significant predictors of successful or unsuccessful maturation at six weeks.(11)

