6. STUDY DESIGN

This is a prospective, single arm, non-randomized, multi-center observational study to record objective data in patients undergoing upper extremity arteriovenous fistula construction with autologous tissue for the purpose of eventual hemodialysis access, in whom the EchoMark implantable marker is placed at the site of vascular anastomosis and the EchoSure module is used to collect ultrasonic data.

The expected duration of this study will be from May 2020 to December 2021. Patients will be identified and recruited by the surgeons participating in the study, who will be determined at a later date. Patients who have been scheduled for creation of an upper extremity autologous arteriovenous fistula creation surgery will be identified as appropriate for study recruitment. The study details will be explained to identified patients and the consent process will begin for willing patients. Participants in the study will have EchoMark devices implanted at the time of the surgery. Monitoring of fistulae will be performed in the postoperative period. Patients who wish to terminate their participation in the research will no longer receive EchoSure ultrasound examinations of their fistula and will revert to the standard monitoring practice of their surgeon.

Stage 1: Patients will be monitored using the EchoSure ultrasound to collect data. Data will be analyzed in an attempt to formulate normative ranges for relevant variables such that clear, objective metrics consistent with healthy versus pathologic fistula healing are established.

Stage 2: Patients will be monitored via EchoSure ultrasound in addition to the standard of care currently followed by the surgeon. Decisions will be made by the vascular surgeon, using a combination of clinical data and the EchoSure data to determine if and when interventions need to be made to prevent failure of fistula maturation. We will then calculate the effect of the EchoMark and EchoSure on the rate of successful fistula maturation.

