10. STUDY PROCEDURES AND METHODS

Patients undergoing fistula creation procedures will be identified. The study will be explained to these patients and informed consent for participation in the study will be obtained from willing patients. A small, FDA-approved tissue marker will be implanted prior to closure of wounds following the Instructions for Use on the FDA-approved labelling.

Stage 1: The fistula will be assessed with intermittent EchoSure examinations, sometimes during routine dialysis visits (maximum 3x/week) to minimize travel. This will conclude when the fistula has entirely matured and the patient begins hemodialysis via the fistula or when the vascular surgeon declares that the fistula has failed despite any and all salvage attempts.

Stage 2: Similar to stage 1 but with implementation of the normative values for relevant variables that resulted from the data collected in stage 1, with subsequent use of the EchoSure flow information in the vascular surgeon's decision making. This stage will also conclude when a year has passed and the fistula is functioning or when the vascular surgeon declares that the fistula has failed despite any and all salvage attempts or that monitoring is no longer clinically necessary.

Actions to Be Taken by Site Staff	Screening and pre-operative evaluation	Clinic Visits	Initiation of dialysis or fistula failure
Consenting	X		
Initial Enrollment Form		X	
Nurse Scan Form		X	
EchoSure Scan		X	
Standard Clinical Exam		X	
End of Trial Period Form			X

11: DATA COLLECTION, ANALYSIS, AND MONITORING

Adverse events are not expected in this study. Unanticipated problems will be reported and discussed with the principal investigator and research coordinator. Patients will be regularly monitored for signs of infection, inflammation or device extrusion. Should the implantable device require removal, it will be removed, and patient will be monitored with conventional methods. The research team will periodically review its protocols to ensure maximal patient safety and data validity.

Source Documentation

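### EchoSure values help decide who is intervened on in Stage 2, so their association with unassisted maturation cannot validate the Stage 1 criteria

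*Combined protocol and SAP*

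**What the plan says.** Section 3 gives Stage 2 two tasks. One is to measure the effect on maturation rates; the other is "to prove the robustness of the fistula maturation failure criteria established in stage 1".

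Section 8, Stage 2, carries out the second task with the coefficient Eta. It takes the "correlation between successful, unassisted maturation and EchoSure-derived values for flow and conduit diameter at two weeks", compares it with the corresponding Stage 1 result, and states that this "will validate the early maturation criteria derived from there". Assisted maturation has its own analysis with a different predictor time: the "correlation between successful, assisted maturation and EchoSure-derived values for flow and conduit diameter immediately following intervention".

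Three other places describe how Stage 2 patients are managed:

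- Section 6: the surgeon decides "using a combination of clinical data and the EchoSure data to determine if and when interventions need to be made".
- Section 10: Stage 2 adds "implementation of the normative values for relevant variables that resulted from the data collected in stage 1". The same sentence then lets the readings shape what the surgeon does: "with subsequent use of the EchoSure flow information in the vascular surgeon's decision making".
- Section 4 presents the two-week time point as "an opportunity to detect and treat maturation failure as early as two weeks postoperatively".

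The readable text does not define unassisted maturation, does not say how a patient with an intervention is coded in the Eta analysis, and describes no masking of the two-week values. A redaction ends the Eta paragraph.

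**The concern.** A validation asks whether a criterion predicts what the fistula would do. Here the criterion's inputs also influence what is done to the fistula, and that action decides whether unassisted maturation remains possible. A fistula with low two-week flow that is intervened on for that reason cannot be an unassisted success, even if it would have matured untouched.

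At stake is the robustness claim in section 3. If treated patients count as not matured unassisted, a criterion that sends healthy fistulas to intervention gains apparent accuracy by doing so. If they are left out, the patients the criterion is about are the ones removed. Either way the Stage 2 coefficient mixes the physiology with surgeons' use of the device. A different coefficient or test would not separate the two.

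**Working it through.** **The plan's own figure.** The Stage 2 size is for the χ² comparison of maturation, 50% against 78%. With two-sided α 0.05, power 0.80 and no continuity correction:

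n = [1.96·√(2·0.64·0.36) + 0.842·√(0.50·0.50 + 0.78·0.22)]² / 0.28² = (1.330 + 0.546)² / 0.0784 ≈ 45 per stage, and 45/0.75 = 60.

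This reproduces. It does not involve the Eta analysis, so the point does not touch the sample size.

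**Inputs for the check.** From section 8: n = 45 evaluable, 50% natural maturation, α 0.05, odds ratio 2.5. Assumed, because the documents do not give them: flow scaled to a standard normal; the lowest 25%, 30% or 50% flagged; intervention probability *a* if flagged and *b* if not; the odds ratio read as per SD of flow.

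**Coding A: treated patients count as not matured unassisted.** Let flow have no relation to natural maturation. The outcome rate is then 0.5(1−a) below the cut-off c and 0.5(1−b) above it. With q the share flagged and φ(c) the normal density at c:

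- overall rate p = 0.5·[1 − q·a − (1−q)·b]
- Eta = 0.5·(a−b)·φ(c) / √[p(1−p)]

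For 30% flagged, all treated and nobody else treated: φ = 0.3477 and p = 0.35, so Eta = 0.1738/0.4770 = 0.36. For half flagged on the same terms: φ = 0.3989 and p = 0.25, so Eta = 0.1995/0.4330 = 0.46. For 30% flagged with a = 0.5 and b = 0.1: p = 0.39, so Eta = 0.0695/0.4877 = 0.14.

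The share of simulated 45-patient trials with a two-sided p below 0.05 for this useless predictor is below. Entries move by a point or two between runs.

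| Flagged | a / b | Eta | Significant |
|---|---|---|---|
| 25% | 0.3 / 0.1 | 0.06 | 7% |
| 25% | 1.0 / 0 | 0.33 | 61% |
| 30% | 0.3 / 0.1 | 0.07 | 7–8% |
| 30% | 0.5 / 0.3 | 0.07 | 7–8% |
| 30% | 0.5 / 0.1 | 0.14 | 15% |
| 30% | 0.5 / 0 | 0.18 | 20–22% |
| 30% | 1.0 / 0 | 0.36 | 73–74% |
| 50% | 0.3 / 0.1 | 0.08 | 8% |
| 50% | 0.5 / 0.1 | 0.17 | 20% |
| 50% | 0.8 / 0.1 | 0.31 | 57% |
| 50% | 1.0 / 0 | 0.46 | 94–95% |

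**Coding B: treated patients excluded.** In the same null scenarios the mean correlation stays near 0 and about 5% of trials are significant. There is no false signal.

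**Flow truly predictive (odds ratio 2.5 per SD).** With no interventions, Eta is 0.388. With interventions:

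| Flagged | a / b | Coding A | Coding B |
|---|---|---|---|
| 25% | 0.3 / 0.1 | 0.381 | 0.378 |
| 25% | 1.0 / 0 | 0.532 | 0.289 |
| 50% | 0.3 / 0.1 | 0.396 | 0.386 |
| 50% | 0.8 / 0.1 | 0.524 | 0.337 |
| 50% | 1.0 / 0 | 0.630 | 0.225 |

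Coding A mostly inflates the true association, though it can lower it slightly (0.381). Coding B attenuates it. Under full adherence with half flagged, the same physiology is reported as 0.63 or 0.23 depending on an unstated rule.

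**The case against.** A reader might infer that two-week flow will look predictive whatever the truth. The documents do not support that. The false signal needs coding A. Because section 8 analyses assisted maturation separately and from a different time point, it can be read as confining the unassisted analysis to fistulas without an intervention. That reading removes the false signal and leaves attenuation. This stands, and it is why the point has to be put under both codings.

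The large percentages need every flagged patient treated and nobody else. Section 6 says decisions combine clinical and EchoSure data, and with mixed decision-making the rate is nearer 7–20%. This also stands. However, Stage 2 exists to act on EchoSure, so the bias grows as the programme works as intended.

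A reader might also conclude that the validation cannot fail. The plan compares Stage 2 with Stage 1 and does not state a test of Eta against zero. A useless predictor would tend to show nothing in Stage 1, so an inflated Stage 2 value could disagree with it. The percentages above therefore measure the false signal, not the planned comparison. Even so, agreement or disagreement with a coefficient biased by an unknown amount cannot settle whether the criteria hold.

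Lastly, the redacted text could contain a coding rule or safeguard. That cannot be excluded, though sections 6 and 10 describe open use of the values.

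**Conclusion.** The Stage 2 association with unassisted maturation cannot validate the Stage 1 criteria or show them to be robust, because EchoSure-informed intervention helps determine the outcome. The direction of the bias depends on a coding that the readable plan does not give. Under coding A a useless predictor is significant in about 7–8% of 45-patient trials when EchoSure weakly drives decisions, and in 61%, about 73% or 94% under full adherence with 25%, 30% or 50% flagged. Under coding B the rate is about 5%, and a true Eta of 0.388 falls to between 0.386 and 0.225. All of this rests on assumed flag rates, intervention rates and a per-SD odds ratio.

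It should be fixed, but it does not undermine the main Stage 2 result. A reader might extend it to the primary endpoint, which is the maturation or failure rate compared by χ². That comparison does not use the Eta analysis.

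Nor do the documents support Stage 1 as a clean substitute. Section 10 allows salvage attempts there and states no masking. The Stage 1 outcome in section 8 is successful maturation, not restricted to unassisted, so the two stages' coefficients also refer to different outcomes. Relying on Stage 1 alone would leave cut points derived in about 45 patients without any independent check.

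**What to change.** - In sections 3 and 8, replace the statements that Stage 2 validates the criteria or proves their robustness with a statement that the association is descriptive.
- Define unassisted maturation and pre-specify how patients with an intervention are coded. Report the association both ways (treated coded as not matured unassisted, and treated excluded), each with an interval and the expected direction of bias.
- Add two case report form items: what triggered each intervention (EchoSure value, clinical finding or Duplex finding) and whether a lesion was found. The schedule in section 10 lists no form dedicated to interventions. Report both items descriptively. Do not use a found lesion to redefine a true positive, since that swaps maturation failure for another outcome, confirmed only in those worked up.
- Present the Stage 1 estimates as the less affected evidence, noting that Stage 1 allows salvage and uses a different outcome.

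The cost is some analysis-plan wording, one extra tabulation and two form items that must be collected prospectively. Patient management does not change. The downside is a more modest claim about the criteria.
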